We hypothesize that therapy done at a low dose will produce the best cost-to-risk ratio for patients.

3. Research design and procedures

This study is designed as a randomized controlled trial with repeated measures.

Aim – the effect of exercise dose on pain: subjects will be randomly assigned to one of four exercise groups: 1.) no exercise (control); 2.) low dose exercise (3x/week); 3.) moderate dose exercise (5x/week); 4.) high dose exercise (10x/week).

The co-primary investigators (co-PI's) will be involved in the procedures listed below. Graduate research students will assist with recruitment, data collection, and data processing. A PhD student in the Biology department ([name]) will assume primary responsibility for data collection. The graduate students will be trained on all procedures involved in this study by the co-PI's. Prior to data collection, the prospective subjects will complete a full screening, using a checklist of the inclusion/exclusion criteria and the PAR-Q and AHA health questionnaires (see Instruments) to determine eligibility. The purpose of the study, the methods of data collection and all potential risks will be verbally communicated to prospective subjects at the

initiation of the first data collection session (Day 0) (Figure 1). Prospective subjects will be given an approved informed consent form to read and sign. Subjects will then complete the International Physical Activity Questionnaire long form (IPAQ-long) to assess baseline level of daily physical activity and the Social Interaction Anxiety Scale (SIAS) for a measure of participant's anxiety. The researcher will explain the questionnaires to subjects and will be available to answer any questions while the subjects complete these forms. Basic health information obtained from the subject will assess whether the subject has been diagnosed with any cardiac, respiratory, neurological or musculoskeletal disorder, chronic pain or currently has acute pain. Subjects who report any of the above medical diagnoses or pain during screening will be excused from participation in the study, but will receive compensation for attending the screening session. Any identifying information used to determine eligibility, including the checklist of inclusion/exclusion criteria and the health questionnaires, will be destroyed.

[figure not shown]

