The collection of data has been described in detail under "Procedures". The primary outcome is a change in Quantitative Sensory Testing. This includes a series (8) of Quantitative Sensory Tests measured at baseline and at the completion of the 1-week intervention period. These tests are measured at two sites (calf and forearm). Significant differences between groups for 7 of the tests (per body site) will be identified using a one-way ANOVA comparing percent change from baseline (post-test (i.e. day 6)/baseline test (i.e. day 0)). Given the number of statistical tests that will be required for the primary outcome measurements, $p < 0.01$ will be utilized for each body site. An additional test for mechanical sensitivity will be measured at each site using a rank sum test at $p < 0.05$.

The secondary outcomes for this study include (1) HR during exercise, (2) Borg RPE before and after exercise and (3) testing "acute" effects of exercise on QST testing. HR during exercise and Borg RPE are measured to make sure that exercise causes a change in HR and/or perceived exertion. HR and Borg RPE data will be analyzed using percent change from start of exercise (post-exercise/pre-exercise) with two-way ANOVA for 3 treatment groups (3-day, 5-day, 10 day) across time (day 1, 3, 5) with an adjusted p value of $p < 0.03$. Control group will not be included in that analysis as HR was not measured on the control days and perceived exertion is at "0" on all days. For acute effects of exercise, participants were given 8 QST tests (on each forearm and calf) 5 min and 30 min after each exercise (or control session) on days 1, 3, and 5. Significant differences between groups for these tests (per body site) will be identified using a two-way MANOVA comparing percent change from baseline (post-exercise/baseline test (i.e. day 0)) across the three days (day 1, day 3, day 5) and at the 5 min and 30 min time QST measuring point. Given the number of statistical tests ($n=8$) that will be required for the QST secondary outcome measurements, $p < 0.01$ will be utilized for each body site.

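### The acute QST analysis names a two-way MANOVA for three factors, two of them within subject, and appears to put the rank-tested filament measure into a normal-theory model

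*Combined protocol and SAP*

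**What the plan says.** Section 3 sets up the factors. In its words, "subjects will be randomly assigned to one of four exercise groups", and "This study is designed as a randomized controlled trial with repeated measures". Pain and sensory measures are taken after exercise or rest on days 1, 3 and 5, at 5 and 30 minutes.

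Section 8 lists the acute effect on QST as the third secondary outcome. It states the aim as "Significant differences between groups for these tests (per body site) will be identified". The method is a "two-way MANOVA comparing percent change from baseline (post-exercise/baseline test (i.e. day 0)) across the three days" (days 1, 3 and 5) "and at the 5 min and 30 min time QST measuring point". Eight tests are counted, and p < 0.01 applies at each body site.

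For the primary outcome (day 6 against day 0), the same section divides the series of eight tests differently. Seven go to a one-way ANOVA of percent change. For the remaining one: "An additional test for mechanical sensitivity will be measured at each site using a rank sum test", at p < 0.05. The acute paragraph makes no such exception.

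**The concern.** A two-way label does not fit a comparison of group, day and time point. The section names no subject effect or within-subject error term, so the sentence can be run in more than one way. In one version the subject is the unit of analysis and the error rate is correct. In another, each subject-day is a separate row and the between-group test is too liberal, because the rows from one person are correlated. Two analysts following the same sentence could reach opposite conclusions about whether groups differ.

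The second issue is the outcome type. The filament threshold is the force of one filament from a fixed set, so it moves in steps. The plan ranks it on day 6, yet appears to model its percent change by normal theory on days 1, 3 and 5, with no reason given for the difference.

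**Working it through.** **Factors.** Group has 4 levels (between subjects), day 3 and time point 2 (both within subject). Each person gives 3 x 2 = 6 correlated post-session readings per test and site.

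**How the plan uses the term elsewhere.** In the preceding sentences of Section 8, the two-way ANOVA for heart rate and Borg RPE crosses treatment group with day. Carried over to the acute QST analysis, this gives group by day, with the 5- and 30-minute readings as the two outcomes.

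**Error rate of the group test.** The plan's only figure here is the nominal 0.01. I simulated 4 groups x 3 days x 2 time points with no true effect and equal correlation among a person's six readings, 4,000 runs per setting. MANOVA tests used Wilks' lambda with Rao's F. Group sizes of 10 (minimum) and 15 (target) come from Section 5. The correlation is an assumption; the documents give no value.

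| Analysis of the group effect, nominal 0.01 | n per group | corr. 0.3 | corr. 0.5 | corr. 0.7 |
|---|---|---|---|---|
| Group x day MANOVA, subject-days as independent rows | 10 | 0.068 | 0.119 | 0.162 |
| Same | 15 | 0.079 | 0.122 | 0.167 |
| Subject means over the six occasions | 10 | 0.009 | 0.010 | 0.010 |
| MANOVA with the six occasions as outcomes, one row per subject | 10 | 0.010 | 0.011 | 0.010 |

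The Monte Carlo standard error is sqrt(0.01 x 0.99 / 4000) = 0.0016 near 1%, and sqrt(0.162 x 0.838 / 4000) = 0.0058 at the largest value in the 10-per-group row. As a check, at zero correlation the first analysis gives 0.010 at 10 per group. Going from 10 to 15 per group does not remove the inflation.

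With subject-days as independent rows, the day and group-by-day tests err the other way. At 10 per group they reject in 0.0018 to 0.0032 and 0.0008 to 0.0018 of runs over the three correlations, so they lose power.

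**Which tests are included.** In the primary analysis, 7 by ANOVA + 1 by rank sum = 8. The acute analysis also counts 8, so mechanical sensitivity appears to be among them.

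**What the filament measure looks like.** Section 3 gives forces from 0.008 g to 1.0 g, one force per filament. The range is 1.0 / 0.008 = 125-fold. A post/baseline ratio can therefore in principle take values from 0.008 to 125, in discrete jumps.

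**The case against.** The strongest defence is that a valid reading exists. The trial is described as a repeated-measures design, and MANOVA is a standard method for such data. Day and time point could be the two within-subject factors, with group between subjects. That drops no factor, assumes no independence, and holds about 1% in the simulation. This stands, and it is why the right word for the factor structure is under-specified rather than wrong. It does not settle the matter, because the text does not say this and the nearest use of the same term means group by day.

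A reader might go further in two ways that the documents do not support.

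- One might infer that the model cannot be fitted, because 8 tests x 6 occasions = 48 outcomes exceed the 4 x (10 - 1) = 36 error degrees of freedom. But Section 8 counts eight statistical tests per site, which implies one model per test. The largest such model has 6 outcomes against 36 degrees of freedom and can be computed.
- One might treat all six readings as independent and quote a type I error of about 20%, 34% and 46% at the same three correlations. That is a univariate three-way ANOVA, which the plan does not name.

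On the filament test, the defence is that the acute paragraph never names it. Its inclusion rests on the count of eight and on the name given in the primary analysis. The count is itself uncertain: the procedures give 1 filament, 1 heat latency, 2 heat VAS, 1 pressure threshold and 2 or 4 pressure VAS measures, so 7 or 9. The plan also gives no reason for its rank test. These points make the inclusion an inference, but the unexplained difference between the two analyses remains.

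**Conclusion.** The acute QST analysis is under-specified, and the meaning the plan gives to two-way elsewhere points to a version that does not control error. Under group by day with independent subject-days, the group test runs at about 7%, 12% and 16% instead of 1%, for assumed correlations of 0.3, 0.5 and 0.7, equal correlation across occasions and 10 per group. If the intended analysis keeps the subject as the unit, there is no inflation.

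The filament inconsistency does not depend on how the MANOVA is read, but it does depend on the inference that the eight tests include that measure. I put no figure on its effect.

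The point concerns a secondary outcome. The day 6 primary analysis is not affected.

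**What to change.** Replace the sentence in Section 8 as follows.

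1. List the eight tests by name, so that it is clear which seven are treated as continuous.
2. For each of the seven, at each body site, specify one of two models. The first is a repeated-measures MANOVA with group between subjects and day and time point within subject. The second is a mixed model with group, day, time point and their interactions, plus random effects for subject and for day within subject, or an unstructured covariance over the six occasions. A subject effect alone is not enough, because the 5- and 30-minute readings share a day. With day-level variance assumed at 0.5 or 1 times the residual, simulation (10,000 runs, 10 per group) put the group-by-day test at 6.1% or 11.5% at nominal 1% under a subject effect alone; the group main effect stayed at about 1%.
3. Name the group main effect as the one test read against p < 0.01. Report interactions as descriptive.
4. Analyse the filament threshold separately, either by a rank test across the four groups (for example on each subject's mean change) or on log force.

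The cost is analysis wording and standard software. No new data are needed.

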Pressure Algometer –

For pressure pain testing, we will use a standard mechanical pressure algometer (Wagner Instruments).

Anxiety measures

All groups will be assessed for anxiety with questionnaire methods using the Social Interaction Anxiety Scale (SIAS)¹⁶. The SIAS measures anxiety with respect to social interactions. It is one of the more often-used self-report measures of social anxiety, with numerous evidence-based studies demonstrating its reliability and construct validity¹⁷. The SIAS contains 20 items which are rated from 0 (not at all characteristic or true of participant) to 4 (extremely characteristic or true of participant). Items are self-statements describing one's typical cognitive, affective, or behavioral reaction to a variety of situations requiring social interaction in dyads or groups (e.g., going to a party, talking to an attractive member of the opposite gender, expressing one's feelings).

5. Sample selection and size

Healthy adults will be recruited for participation in this study. The PAR-Q and You form and the AHA screening questionnaire will be administered during the screening process to determine whether potential subjects meet the inclusion/exclusion criteria.

Inclusion criteria include:

- Between age 18-40
 - Normal BMI (18.5-25)
 - HR 60 to 100
 - BP less than or equal to 140/90
- *HR and BP will be taken as part of the screening process to determine eligibility and also taken at the beginning of each exercise session.

Exclusion criteria include as indicated by the PAR-Q and You and AHA screening forms:

- Age less than 18 or greater than 40 years
- Cardiac, respiratory, neurological or musculoskeletal disease
- Acute pain
- Chronic pain condition
- Diabetes
- BMI ≥ 25.1 or ≤ 18.4
- Regular participation in high intensity athletic/sporting activities
- Sedentary
- Anxiety or depression disorders.
- Tape allergy
- Currently pregnant

A power analysis of pain outcome indicates that a minimum of 10 people/condition will be sufficient to detect statistical differences in our primary dependent variable (pain sensitivity), but to account for variability, our recruitment goal is 15 people/condition. When 10 participants per group have completed the study, a preliminary analysis will be conducted for statistical power, if we reach 0.80, recruitment will stop.

6. Recruitment of subjects

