The following demographic variables will be collected and compared between groups to further check against potential bias; age, handedness, body mass index (BMI), baseline heart rate (HR), baseline blood pressure (BP), baseline IPAQ-short, and STAI (state-trait anxiety). A significant difference in the proportion handedness will be tested using the Chi-Square test where a $p < 0.05$ will be considered significant. All other continuous variables will be tested using the one-way ANOVA to test for significance differences between the four study groups ($p < 0.05$).

9. Dissemination of Results

Results of this study will be submitted to a peer-reviewed journal for publication and will be available to the public.

10. Emphasize issues relating to interactions with subjects and subjects' rights

Subjects will be notified of their rights, all risks and benefits of participation in this study during the informed consent procedure. Subjects will be informed that they may withdraw from participation at any time. Data collection sessions will be scheduled at times that are mutually convenient for the subject and the researchers and all efforts will be made to work with the subject's schedule. All personal and health information will be kept confidential as data will be coded. Identifiers will be stored in a locked filing cabinet and all coded data will be stored in either a separate locked filing cabinet or a password protected computer. Only researchers and staff directly involved on this study will have access to this information. Health information obtained for this study will come directly from the participant and not their healthcare providers

or medical records. This information will be obtained during screening occurring in the Rangos School of Health Sciences exercise physiology lab and therefore is not under HIPAA.

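### Seven baseline significance tests serve as a bias check that often flags chance, passes most sizeable imbalances and leads to no stated action; describe baseline and prespecify covariates instead

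*Combined protocol and SAP*

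**What the plan says.** The last paragraph of section 8 (Collection of data and method of data analysis) sets out the baseline comparison: "The following demographic variables will be collected and compared between groups to further check against potential bias". Seven variables are listed: age, BMI, handedness, heart rate, blood pressure, an IPAQ-short score and the STAI. For handedness, the "proportion handedness will be tested using the Chi-Square test" at p<0.05. For the rest, "All other continuous variables will be tested using the one-way ANOVA", also at p<0.05, across the four groups.

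Three other parts of the plan bear on this:

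- **Allocation.** Section 3 states that "subjects will be randomly assigned to one of four exercise groups".
- **Size.** Section 5 gives a minimum of 10 and a goal of 15 people per condition.
- **Primary analysis.** Section 8 compares the Day 6 to Day 0 ratio between groups by one-way ANOVA for seven tests per body site at p<0.01, and mechanical sensitivity by a rank sum test at p<0.05. No baseline covariate enters. The Day 0 value acts only as the denominator of the ratio.

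The stricter threshold for the outcome tests is justified by their number. No such allowance is made for the baseline tests. Nothing states what follows a significant or a non-significant baseline result.

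**The concern.** After sound randomisation, baseline differences between arms are due to chance, so a p-value cannot measure bias. What matters for the Day 6 comparison is how large an imbalance is and whether the variable predicts the pain outcome. A test at 10 to 15 per arm addresses neither.

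The check can therefore mislead in two directions. Several tests at 0.05 will fairly often produce a significant result by chance alone. In small arms, quite large chance differences will usually come out non-significant. With no action attached, a pass may be taken as evidence of balance, and a flag may prompt adjustment chosen after the data are seen. Meanwhile, baseline information that the trial already collects is not used to sharpen the primary comparison.

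**Working it through.** **Inputs from the plan.** Four randomised groups (section 3). 10 or 15 per group (section 5). Seven baseline variables, each at 0.05 without adjustment (section 8). The plan gives no error rate or power for the baseline tests, so there is no figure of its own to reproduce. The 10 per condition comes from a power analysis of the pain outcome whose effect size and SD are not given, and it says nothing about these tests.

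**Assumptions, not in the plan.** Blood pressure may be one test or two (systolic, diastolic), and so may STAI (state, trait), giving 7 to 9 tests. Correlation among the continuous variables is taken as 0 to 0.5. For the simulations, 10% of subjects are left-handed. The continuous variables are normal with equal variance.

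**Step 1: chance of at least one significant baseline result under sound randomisation.** For k independent tests this is 1 − 0.95^k.

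| Tests | Formula | Result |
|---|---|---|
| 7 | 1 − 0.95^7 | 30.2% |
| 8 | 1 − 0.95^8 | 33.7% |
| 9 | 1 − 0.95^9 | 37.0% |

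Simulation with the small-sample chi-square for handedness and correlation from 0 to 0.5 gives 24–29% for seven tests and 28–36% for nine, over both arm sizes. The overall range is about 24–37%.

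**Step 2: how often a sizeable chance gap arises.** Take one continuous variable and the gap between the highest and lowest arm means, in units of the pooled within-arm SD. Multiplied by √n, this gap follows the studentized range distribution for 4 groups with 4(n − 1) degrees of freedom. The 0.5 SD threshold is an illustration, since the plan names no imbalance that would matter.

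- n = 10: 0.5 × √10 = 1.58 on 36 df, so P(gap > 0.5 SD) = 68%.
- n = 15: 0.5 × √15 = 1.94 on 56 df, so P(gap > 0.5 SD) = 52%.

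**Step 3: how many of those gaps the ANOVA leaves unflagged.** Significance needs the between-arm sum of squared deviations of the means, in SD units, to exceed 3F/n, where F is the 5% critical value. For a given gap R, that sum is at most R² (two arms at each extreme). So a significant result requires R > √(3F/n).

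- n = 10: F(3, 36) = 2.87 and √(3 × 2.87/10) = 0.93 SD.
- n = 15: F(3, 56) = 2.77 and √(3 × 2.77/15) = 0.74 SD.

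Every significant result therefore lies among the gaps above 0.5 SD, and significant results make up 5% of all trials.

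- n = 10: flagged 0.05/0.681 = 7.3%, unflagged 92.7%.
- n = 15: flagged 0.05/0.524 = 9.5%, unflagged 90.5%.

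Simulation gave the same figures (92.7% and 90.4%).

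**Step 4: effect on the primary analysis.** The baseline tests feed into no other analysis in section 8. As written, they leave the error rate of the Day 6 ANOVA unchanged.

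**The case against.** The strongest reply is that nothing in the trial's inference is shown to be wrong. The baseline tests drive no decision, and an unadjusted comparison of randomised groups already allows for chance imbalance in its error rate. That stands. A reader might infer that the tests inflate the primary type I error, or that leaving Day 6 unadjusted biases it. The documents support neither: the most that is lost is precision.

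A reader might also infer that these tests are the trial's only protection against bias. The plan's own word, that they are to check further, shows that randomisation is the main protection. They are, however, the only check of baseline balance described.

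A third point is that sections 3 and 8 describe no sequence generation or concealment, so a baseline test might signal faulty allocation. That is a legitimate but limited use. The plan does not state it as the purpose, and nothing in the documents suggests that allocation failed.

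It is also fair that the harms are possible rather than documented. No text says that a non-significant result will be read as absence of bias, or that covariates will be picked from these p-values. Equally, no text rules this out.

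Finally, the documents do not show that activity or anxiety predicts the percent change. Section 5 narrows both ranges by excluding sedentary people, regular high-intensity athletes and people with anxiety disorders. This limits the gain that can be claimed from adjusting for them.

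**Conclusion.** The point holds as a minor one. The baseline tests cannot do the job given to them. Under sound randomisation they produce at least one significant result in about 24–37% of trials (30% for seven independent tests). For each continuous variable they also leave unflagged more than nine in ten of the chance gaps above 0.5 SD between the extreme arms.

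The first figure rests on the number of tests counted and their correlation. The second rests on normality, equal variance and the illustrative 0.5 SD threshold. Neither describes damage to the primary result. The consequences are false reassurance or false alarm, room for unplanned adjustment, and whatever precision is forgone by not using baseline data at Day 6. The documents give no correlation between baseline and outcome, so that last item is not quantified.

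**What to change.** 1. Remove the baseline p-values from section 8. Report each variable by arm, as mean and SD or as counts.
2. Prespecify a small covariate set for the Day 6 model of the seven ANOVA-analysed tests at each body site, to be used whatever imbalance is observed. Put the Day 0 value of the test concerned first, then the baseline activity and anxiety scores.
3. Before naming those scores, reconcile the instruments. Sections 3 and 4 describe IPAQ-long and SIAS, while section 8 lists IPAQ-short and STAI.
4. Leave the rank sum test of mechanical sensitivity unadjusted, since it takes no covariate.

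**Cost.** Items 1 and 3 change only wording. Item 2 turns the one-way ANOVA into an analysis of covariance and uses one error degree of freedom per covariate, out of 4 × (10 − 1) = 36 at the minimum size or 4 × (15 − 1) = 56 at the goal. Three covariates would leave 33 or 53. A covariate that does not predict the outcome costs a little power. One that does predict it can repay that cost, by an amount that cannot be stated from the documents.
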